- 3.1. This is a prospective, open-label, randomized, single center, controlled clinical study to determine the effect of intraoperative infusion of NS versus Isolyte on post-cardiac surgery on AKI event (renal injury) as measured by urinary [TIMP-2]*[IGFBP7] levels. After informed consent, we will randomly assign 30 trial-completing participants (potentially enrolling up to 40 to account for any dropouts) to the two study arms in a 1:1 ratio. We will compare the effect of electrolyte solution on patients' post- vs. preoperative [TIMP-2]*[IGFBP7] score differences with pairwise t-tests, and will similarly analyze routine demographic data and potential confounders, as well as secondary outcomes as listed below.
- 3.2. This is an open-label trial.

4. Inclusion and Exclusion Criteria

- 4.1. Participants will be drawn from the population of adult patients undergoing cardiac surgery at UNMH.

The Impact of Low Chloride Containing Fluids on Acute Kidney Injury after Cardiopulmonary Bypass as Assayed by Urinary [TIMP2]*[IGFBP7]

- 4.2. Inclusion criteria: consenting adult male and female patients undergoing non-emergent on- and off-pump cardiac surgery including: bypass grafting, valvular procedures, congenital defect correction, and thoracic aortic procedures or a combination of these procedures.

Exclusion criteria: emergency surgery, pregnancy, previous renal transplantation, documented moderate to severe AKI prior to enrollment (e.g. RIFLE-I or RIFLE-F/KDIGO stage 2 or 3), patients already receiving dialysis (acute or chronic) or in imminent need of dialysis at time of enrollment, subjects with chronic kidney disease without baseline serum creatinine value (baseline within 6 months of enrollment).

- 4.3. This study does not involve adults unable to consent, individuals who are not yet adults, pregnant women, or prisoners.
- 4.4. We will not exclude particular populations such as women, children, persons not fluent in English, any particular racial or ethnic groups, etc.

5. Number of Subjects

- 5.1. This is not a multicenter study; all recruitment will occur at UNMH.
- 5.2. We plan to recruit sufficient participants to obtain complete data on 30 subjects (15/group). We do not anticipate a high withdrawal rate, but may recruit as many as 40 to have a complete dataset of this size. Recruitment will stop upon attainment of the full sample of 30, or with the 40th consenting patient who at least begins study treatment (whichever comes first).

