- 5.3. A power analysis with G*Power 3.1.9.2 software indicates that n=30 is sufficient in the context of a t-test to detect a difference between groups for the primary outcome that is roughly equal to the sample standard deviation. For (purely hypothetical) example, if the mean is 100 units and roughly 2/3 of the sample falls between 95 and 105, we would have 80% power to detect a treatment difference of 5 units.

6. Study Timelines

- 6.1. All data collection will occur in conjunction with clinically-indicated surgical care. The existence of this study will not affect the decision to refer for surgery, or the subsequent decision to proceed or not proceed with surgery, for any patient.
 - Data collection will include pre-operative serum creatinine levels, which are very likely to already have been recorded for clinical reasons. The maximum pre-operative interval for this value will be six months (it is extremely unlikely that sufficiently recent serum creatinine data will be unavailable, but if this is the case, this value will be obtained prior to surgery). Other data will be gathered immediately prior to surgery, immediately after surgery, and up to 48 hours postoperatively. It is anticipated that all participants will already be in the hospital for all data collection.
 - A recruitment period duration of one year should be sufficient to recruit the targeted participant sample; we will apply for continuing review prior to study expiration if the target sample size is not met at that time.

The Impact of Low Chloride Containing Fluids on Acute Kidney Injury after Cardiopulmonary Bypass as Assayed by Urinary [TIMP2]*[IGFBP7]

- Upon completion of data collection, the investigators anticipate one year for completion of all analyses, manuscript/presentation preparation, and submission of scholarly product to relevant outlets.

7. Study Endpoints

7.1. The primary outcome is the change in urinary [TIMP2]*[IGFBP7] composite from baseline to 24 hours postoperatively.

The secondary outcomes are:

- serum creatinine preoperatively and postoperatively at 24 and 48 hours,
 - serum chloride preoperatively and postoperatively at 24 and 48 hours,
 - clinically-determined need for dialysis prior to discharge, and
 - arterial pH, measured 24 hours after surgery.

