safety of normal saline vs. Isolyte for cardiac surgery patients, or the extent to which they may or may not reduce kidney-related complications of surgery.

- 18.2. Both normal saline and Isolyte are in widespread use for fluid replenishment during surgery, with excellent safety records.
- 18.3. Risks to embryos and fetuses are not relevant here; pregnancy is an exclusion criterion.
- 18.4. There are no appreciable risks to others who are not subjects.
- 18.5. Steps taken to minimize the probability or magnitude of risks include: selection of FDA-approved IV fluids for the study, the open-label nature of the study, permitting provider discretion in amounts administered, gathering as much study data as possible from the already-existing medical record, maintaining routine labwork to forewarn providers of developing kidney problems, and exclusion of patients known to have kidney problems.

19. Potential Benefits to Subjects

- 19.1. We have not identified any benefits that will accrue to all subjects. If one of the two IV fluids is superior to the other, patients randomized to receive it may experience benefit. The existence and nature of these benefits is not currently known, but because both normal saline and Isolyte are currently in widespread use for intraoperative fluid maintenance without known major problems, any benefit is expected to be small and only detectable at the group level.

20. Recruitment Methods

- 20.1. Potential subjects who are already inpatients will be recruited in patient rooms at UNMH the night before surgery. For patients who arrive at the hospital on the day of surgery, recruitment will occur in the pre-operative holding areas.
- 20.2. Investigators will identify potential subjects from their regularly-scheduled case load, and apply the inclusion/exclusion criteria to the extent possible prior to making research-related contact with a patient.
- 20.3. No recruitment materials are planned. Potential participants will be provided a copy of the consent form for their review and consideration during the recruitment process. Consenting participants will be provided a copy of the completed form.

21. Provisions to Protect the Privacy Interests of Subjects

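### Assignment is tied only to consent, with nothing to conceal the next arm and no rule placing its release after the baseline urine; patients lost once the arm is known are dropped and replaced

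*Combined protocol and SAP*

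**What the plan says.** - **Assignment.** Section 3.1: "After informed consent, we will randomly assign 30 trial-completing participants", "to the two study arms in a 1:1 ratio". Section 12.1 repeats that consenting patients are randomised. Neither section, nor any other, describes how the sequence is generated, who holds it, whether it is blocked, how it is concealed, or when after consent the arm is released.
- **Blinding.** Section 3.2: "This is an open-label trial".
- **Who recruits.** Section 20.2: "Investigators will identify potential subjects from their regularly-scheduled case load"; 8.2 says the same of their routine patients. Under 25.1.1 study team members obtain consent.
- **When consent occurs.** Section 20.1: "Potential subjects who are already inpatients will be recruited in patient rooms at UNMH the night before surgery"; same-day arrivals are approached in the holding area. Section 25.1.4 lets inpatients think it over until morning, and 21.1 mentions only the holding area.
- **When baseline is taken.** Section 6.1, after dealing with preoperative creatinine: "Other data will be gathered immediately prior to surgery". Under 7.1 the primary outcome is the change in the urinary index from baseline to 24 hours.
- **Who is counted and analysed.** Under 5.2 recruitment ends at 30 complete datasets (15 per arm) or "with the 40th consenting patient who at least begins study treatment". Under 15.2 data collection stops at withdrawal. Under 15.3 patients who leave their arm and have the fluid changed are removed from data collection. Under 15.4 complete withdrawals are left out of the analysis.

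**The concern.** Concealing the next assignment is a separate matter from blinding, and it can be done in an open-label trial. Without it, two routes to selection are open.

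The first is before enrolment. A recruiter who can see past arms and anticipate the next one can decide whom to approach, and when, with the arm in mind. Eligible operations run from off-pump grafting to thoracic aortic procedures (4.2), so that choice could matter for kidney risk. Section 13.1 plans an unadjusted two-group test.

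The second is after disclosure. If the arm is known overnight, a patient may withdraw, be taken out, or miss the baseline sample before any fluid is given. Such a patient has no complete dataset, does not count toward the cap and is replaced. Because data collection stops at withdrawal, those outcomes may not exist for a later analysis by assigned arm.

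**Working it through.** **1. Order of events.**

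| Step | Earliest time the text allows | Source |
|---|---|---|
| Inpatient consent | Night before surgery | 20.1, 25.1.4 |
| Assignment | Any time after consent | 3.1, 12.1 |
| Baseline urine | Immediately before surgery | 6.1 |
| First assigned fluid | Not fixed: 12.1 describes it once as intraoperative and once as perioperative | 12.1 |

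No statement places assignment after the baseline sample. For an inpatient who consents in the evening, the text allows disclosure hours before baseline. For one who consents in the morning, or a same-day arrival, the gap may be short or absent.

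**2. Who drops out of the count.** Take a patient who consents, is assigned, and is lost before the first fluid. Under 5.2 this patient is neither one of the 30 nor one of the 40. A patient who starts treatment and then withdraws completely uses one of the 40 places, is omitted under 15.4, and is also replaced. In both cases the analysed 15 v 15 is conditioned on events after assignment. Section 3.1's idea of randomising completers cannot be carried out literally, since completion is unknown at assignment.

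**3. Predictability.** The plan gives no figure on this point. Its only design calculation, 80% power for a difference of about 1 SD (5.3, 13.2), does not bear on allocation. The schemes below are assumptions. A recruiter who knows all past arms and always guesses the arm with fewer assignments so far expects, in a balanced block of 2b, this many correct guesses:

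b + (2^(2b) / C(2b, b) − 1) / 2

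- Blocks of 2: 1 + (4/2 − 1)/2 = 1.5; 1.5/2 = 75%.
- Blocks of 4: 2 + (16/6 − 1)/2 = 2.83; 2.83/4 = 71%.
- Blocks of 6: 3 + (64/20 − 1)/2 = 4.1; 4.1/6 = 68%.
- One 15/15 list: 17.96/30 = 60%.
- One 20/20 list (covering the cap of 40): 23.49/40 = 59%.
- Unrestricted allocation: 50%.

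The shares of assignments known with certainty in advance, if the block size is known, are 50%, 33%, 25% and 6% for blocks of 2, 4, 6 and the 15/15 list.

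Varying the block size does not defeat this strategy, which uses only the running totals. With sizes equally likely, blocks of 2 and 4 give (1.5 + 2.83)/6 = 72%, blocks of 4 and 6 give (2.83 + 4.1)/10 = 69%, and blocks of 2, 4 and 6 give (1.5 + 2.83 + 4.1)/12 = 70%.

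**4. Weight of one patient.** With 15 per arm, replacing one patient by another whose change score differs by 1 SD (an assumption for scale) moves the arm mean by 1/15 = 0.067 SD; two such replacements move it by 2/15 = 0.13 SD. The documents do not say how many such replacements to expect.

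**The case against.** The strongest reply is that this is silence about procedure, not evidence of bad practice. Much of that reply is right, and it limits what can be claimed.

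- A reader might infer that the arm is in fact known before the baseline urine. The documents do not order the two events; both could happen on the morning of surgery. Likewise 25.1.4 and 21.1 allow inpatient consent on the day. Early disclosure is permitted, not prescribed.
- A reader might infer that assigning after consent is itself the fault. It is correct practice, because it keeps the arm from influencing consent. Providers in an open-label trial must also know the arm before they infuse.
- A reader might infer that the clinicians giving the fluid also do the assigning. Section 3.1 speaks of the team as a whole, and 33.1 leaves administration to authorised hospital personnel. No assigner is named.
- The outcome is a laboratory assay, so knowing the arm does not of itself change the baseline value. The route is selection: who is approached, who stays, and whose sample is obtained.
- A guess rate is not a bias in the primary outcome. Section 5.2 also expects few withdrawals.

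What stands is that the text contains no safeguard against either route, and that 5.2 and section 15 actively drop and replace patients lost after assignment. That part is a written rule, not an omission.

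**Conclusion.** The concern holds as a gap that permits selection by arm, not as a demonstration that selection will occur. It is worth correcting before enrolment, because foreseeable allocation and outcomes that were never collected are hard to repair later.

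The size of any bias cannot be computed from the documents. The guess rates, 50% for unrestricted allocation up to 75% for blocks of 2, rest on assumed schemes and on a recruiter who knows every past arm. They serve to compare allocation methods, not to measure bias in this trial. A reader might also infer that sealed assignments alone bring predictability down to 50%. They do not when past arms are visible; of the schemes considered, only unrestricted allocation does.

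**What to change.** **Sections 3.1 and 12.1.** State that the sequence is generated and held by a team member who does not recruit, consent or treat. The Research Information Specialist listed in 9.1 is a candidate, but 9.1 does not say that this person has none of those duties, so this must be confirmed. Release each assignment only after eligibility and consent are recorded and the baseline urine is collected, as close as practical to the first assigned fluid. The two descriptions of the fluid period in 12.1 should be reconciled so that this moment is defined.

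Do not use small blocks, fixed or varying. A single balanced list long enough for the cap, or unrestricted allocation, is less predictable. The price is arms that may not be exactly 15 and 15. A 12/18 split, for example, carries the information of 2 × 12 × 18/30 = 14.4 per arm.

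**Sections 5.2 and 15.** Count every patient whose assignment is released. Analyse by assigned arm all patients whose outcome data can be obtained with consent. Report losses by arm, separating those before and after the first fluid. Drop the wording that randomises completers.

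**Cost.** A little existing staff time, and both fluids must be at hand when the assignment is released. Section 33.1 says both are routinely handled, but does not say that both are stocked where the release would occur. No extra patients, visits or assays are needed.

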33. Drugs or Devices.....	16
Checklist Section	16

1. Objectives

- 1.1. To determine whether the use of a balanced-salt / physiologic level of Cl⁻ crystalloid solution (Isolyte) as compared to NS in cardiac surgery leads to less kidney injury as measured by the composite [TIMP-2]*[IGFBP7] bioassay.

2. Background

- 2.1. Acute kidney injury (AKI) is a potential complication for patients undergoing cardiac surgery. AKI in post-cardiac surgery patients is associated with adverse outcomes, such as prolonged intensive care and hospital stay, diminished quality of life, increased long-term mortality, and an increased risk of chronic kidney disease requiring dialysis.[1-4] The mortality in cardiac surgery patients with AKI severe enough to require renal replacement therapy (RRT) can be as high as 60%.[5]

There are a number of causes and risk factors associated with AKI including poor preoperative cardiac function, diabetes, peripheral vascular disease, and female gender.[6] One of the putative agents associated with AKI in animal models receiving crystalloid fluids for resuscitative interventions is excess exogenous chloride ion (Cl⁻).[7, 8] As compared to non-Cl⁻ containing solutions in animal models, excess Cl⁻ appears to lead to a hyperchloremic metabolic acidosis, increased renal vascular resistance, reduced renal blood flow, and reduced glomerular filtration rate – all of which are injurious to kidney function.[9-11]

In non-cardiac surgery, including kidney transplantation, the use of low-chloride containing crystalloids leads to less acid-base and electrolyte perturbation.[12, 13] In trauma resuscitation, low Cl⁻ containing resuscitation solutions are also associated with more ideal acid-base status.[14]

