- 13.1. The primary outcome involves a composite index: the product of urinary TIMP2 and IGFBP7 values. For a given patient, this index will be calculated for preoperative values and for postoperative values as described above, and the difference between pre- and postoperative index values will be recorded as the primary outcome. A t-test (or Wilcoxon-Mann-Whitney test, in the case of nonnormal distributions) will be used to evaluate the hypothesis. Secondary outcomes that similarly involve pre- vs. postoperative changes in laboratory values (serum creatinine and serum chloride) will be tested in the same fashion. The 24-hour arterial pH data will be assessed with t-test or Wilcoxon-Mann-Whitney as appropriate depending on distribution normality. The clinically-determined need for dialysis prior to discharge will be assessed with Fisher's Exact test.
- 13.2. A power analysis with G*Power 3.1.9.2 software indicates that this sample size is sufficient in the context of a t-test to detect a difference between groups for the primary outcome that is roughly equal to the sample standard deviation. For (purely hypothetical) example, if the mean is 100 units and roughly 2/3 of the sample falls between 95 and 105, we would have 80% power to detect a treatment difference of 5 units.

14. Provisions to Monitor the Data to Ensure the Safety of Subjects

- 14.1. Both normal saline and Isolyte have been used routinely in cardiac procedures for many years, nationally and at UNMHSC, and both have excellent safety records. The PI [name] and co-investigators will conduct an interim review of patient records upon completion of data collection for the 20th participant, in an effort to detect substantial differences in outcomes.
- 14.2. All study data will be reviewed.
- 14.3. Both normal saline and Isolyte have been safely used in cardiac surgery for many years. It is exceedingly unlikely that scientific literature would indicate a substantial difference in risk posed by these two solutions; however, as Chief of Cardiac Anesthesia at UNMH, [name] routinely reviews scientific/medical literature related to cardiac surgery.
- 14.4. Patient records will be reviewed for unusual patterns of morbidity/mortality. In addition, all outcomes will be analyzed with the above-described statistical tests.

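### Section 3.1 calls the primary test a pairwise t-test, which does not fit a two-arm comparison or match sections 5.3, 13.1 and 13.2; name one between-arm analysis throughout

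*Combined protocol and SAP*

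**What the plan says.** Section 3.1 (Study Design) describes the main comparison this way: "We will compare the effect of electrolyte solution on patients' post- vs. preoperative [TIMP-2]*[IGFBP7] score differences with pairwise t-tests". The closing words, "score differences with pairwise t-tests", are the only place where 3.1 names a test. The same sentence adds that the investigators "will similarly analyze routine demographic data and potential confounders", and extends this to the secondary outcomes.

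Section 7.1 defines the endpoint: "The primary outcome is the change in urinary [TIMP2]*[IGFBP7] composite from baseline to 24 hours postoperatively". Section 13.1 (Data Analysis) says that, for each patient, "the difference between pre- and postoperative index values will be recorded as the primary outcome". It then says: "A t-test (or Wilcoxon-Mann-Whitney test, in the case of nonnormal distributions) will be used to evaluate the hypothesis". Serum creatinine and serum chloride changes are to be tested in the same way.

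Section 5.3, repeated in 13.2, states that "n=30 is sufficient in the context of a t-test to detect a difference between groups for the primary outcome", for a difference of about one standard deviation with 80% power. Section 1.1 asks whether the balanced solution "as compared to NS in cardiac surgery leads to less kidney injury".

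None of these sections gives a significance level or says whether the test is one- or two-sided. Section 13.1 does not say that its test is between arms, two-sample or independent.

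**The concern.** In a parallel two-arm trial no patient in one arm is paired with a patient in the other, and two arms leave only one comparison to make. The only natural pairs are each patient's pre- and postoperative values, which the sentence in 3.1 mentions just before the word pairwise. Taken as a paired test, the label would describe a question about whether the index rises after surgery, not whether the rise differs by fluid.

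Section 13.1 does not expressly settle this, because its between-arm meaning has to be inferred. The trial is open-label (3.2), and the investigators analyse all outcomes after the 20th participant (12.1, 14.1, 14.4). In that setting the primary test should be fixed by the text, with no choice left once data have been seen.

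**Working it through.** **Inputs.** 15 completers per arm (5.2); between-group difference of about 1 SD and power of 80% (5.3, 13.2); worked example with a difference of 5 and an SD of about 5 (5.3). Level and sidedness are not stated, so I assume two-sided 5%.

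**Step 1. Which test does the stated power belong to?**

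- Two-sample, normal approximation: z = d√(n/2) − 1.96 = 1 × √7.5 − 1.96 = 2.739 − 1.960 = 0.779, so power is 78.2%. The approximation needs 16 per arm for 80%.
- Two-sample, exact noncentral t (28 df): 75.3% two-sided, 84.8% one-sided. The two-sided test reaches 80% at a difference of about 1.06 SD.
- Paired, one arm of 15, mean change of 1 SD of the change (noncentrality √15 = 3.87, 14 df): 94.9%.
- Paired, all 30 pooled (noncentrality √30 = 5.48, 29 df): 99.96%. Only 10 patients would be needed for 80%.

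The plan's 80% is reproduced, within its own word roughly, by the between-arm test only.

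**Step 2. What would separate within-arm tests do?** Suppose the fluids do not differ and both arms rise by the same amount. If p is the power of one arm's paired t-test (n = 15, two-sided 5%), the chance that exactly one arm is significant is 2p(1 − p). The size of the common rise is assumed.

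| Common rise (SD of change) | p | 2p(1 − p) |
|---|---|---|
| 0.25 | 0.147 | 25% |
| 0.4 | 0.303 | 42% |
| 0.5 | 0.438 | 49% |
| 0.7 | 0.713 | 41% |
| 0.75 | 0.771 | 35% |
| 1.0 | 0.949 | 10% |

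A between-arm test at the assumed level would be significant 5% of the time. The values of 41% to 49% lie near the maximum of 2p(1 − p), which is 50% at p = 0.5; the range over the whole table is 10% to 49%.

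**Step 3. What does baseline adjustment gain?** Let σ² be the variance of the index, equal at both times (assumed), and r the correlation between baseline and 24 hours. The per-patient variance is 2σ²(1 − r) for the change score and σ²(1 − r²) for the baseline-adjusted 24-hour value. The ratio is (1 − r²) / [2(1 − r)] = (1 + r)/2. For assumed r of 0.3 to 0.7 this is 0.65 to 0.85, a reduction of 15% to 35% in the variance of the treatment estimate, before the small loss from estimating one slope.

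**The case against.** The strongest reply is that the protocol, read as a whole, describes only a between-arm test. Section 3.1 itself compares the effect of electrolyte solution on score differences, which is a contrast of change scores between fluids. It applies the same analysis to demographics, which have no pre/post pair, and to secondary outcomes that include a 24-hour pH with no preoperative value. Wilcoxon-Mann-Whitney is a test for two independent samples; the usual fallback for a paired test would be the signed-rank test. The objective and the power statement agree with this reading. Pairwise can also loosely mean a comparison of a pair of groups.

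That reply largely stands on intent. A reader might infer from the label that the primary analysis will not compare the fluids, or that its false-positive rate will be 41% to 49%. The documents do not support either inference: no section plans separate within-arm tests or a conclusion drawn from their disagreement.

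The reply does not remove the inconsistency. The label in 3.1 is still wrong for this design, and 13.1 never states that its test is between arms.

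It could also be objected that baseline adjustment is a different model from the change score in 7.1 and 13.1. On the same scale the difference is slight. If Y1 − Y0 = a + bT + cY0, then Y1 = a + bT + (c + 1)Y0, so the treatment coefficient b is the same whether the change or the 24-hour value is modelled with baseline as covariate.

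**Conclusion.** The primary test is mislabelled in 3.1 and incompletely named in 13.1. The weight is low to moderate, because the intended between-arm test can be recovered from 1.1, 5.3, 13.1 and 13.2 and from the rest of the sentence in 3.1. The sample size is unaffected. The error rates of 10% to 49% describe a misuse that the protocol does not plan, and they rest on an assumed common rise of 0.25 to 1.0 SD and an assumed two-sided 5% level.

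Correcting the text also allows a gain at no cost in data: adjusting for the baseline index would reduce the variance of the treatment estimate to 0.65 to 0.85 of its change-score value, for assumed correlations of 0.3 to 0.7 and equal variances at the two times.

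**What to change.** Use the same statement in 3.1 and 13.1: a comparison of Isolyte with saline between arms, at a two-sided 5% level. Preferably this is the 24-hour index adjusted for the baseline index, with the scale fixed in advance (log scale, or ranks, if the index is skewed). Otherwise, name an independent two-sample test on the baseline-to-24-hour change. Remove the word pairwise. Apply the same wording to serum creatinine and serum chloride, since 13.1 tests them in the same fashion.

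The cost is a small edit to the analysis text in these two sections. If the adjusted or log-scale form is chosen, the description of the change score in 7.1 should be aligned with it. The baseline index is already collected, and no extra patients are needed.
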